6.6 End of Study Visit Day 35 (± 3) or Early Withdrawal

- Identify if any exclusion criteria have arisen (i.e. skin conditions, living conditions/close contacts, pregnancy).
- Vital signs (see section [6.1.2](#)). Assessment of pericarditis/myocarditis symptoms (see section [6.9](#)).
- Urine pregnancy test for female subjects of child bearing potential. In the event of a positive pregnancy test result, the pregnancy must be reported to Emergent and the *National Smallpox Vaccine in Pregnancy Registry*. As a COVID-19 precautionary measure, women of childbearing potential will not be included in the study temporarily. Vaccination site inspection. If the visit cannot be performed in person, the study subject should take a photograph of the vaccination site or show it over live video call to the Investigator who will document the assessment. Photo or live video call will be deleted after assessment.
- Unanticipated problems.
- All adverse events including all cardiovascular adverse events (symptoms and signs).
- Diary card review and verification against AE collection above.
- Concomitant medications (see section [6.10](#)).
- Review vaccination site care instructions and provide vaccination site dressing kit (required only if the scab has not separated) (see section [6.2.3](#)). If the visit cannot be performed in person, the study subject should take a photograph of the vaccination site or show it over live video call to the Investigator who will document the assessment. Photo or live video call will be deleted after assessment.

After the End of Study visit, eligible subjects may have the option to continue donating plasma as per the site's FDA approved SOPs for VIGIV plasma collection.

Note: If a subject's vaccination site has not completely healed by the Early Withdrawal Visit then efforts will be made to follow up with the subject until the vaccination site is completely healed. In addition, efforts will be made to conduct the Day 90 safety follow-up with the subject.

6.7 Extended Follow-up Weekly Visits for Unresolved Adverse Reactions

All related AEs (serious and non-serious) will be followed to resolution or stabilization as applicable. Any vaccination scab that has not separated by 28 days after vaccination should be considered an AE.

If extended follow-up weekly visits are required, they will include:

- Identify if any exclusion criteria have arisen (i.e. skin conditions, living conditions/close contacts, pregnancy) (required only if the scab has not separated).
- Assessment of pericarditis/myocarditis symptoms (see section [6.9](#)).
- Urine pregnancy test [females of childbearing potential (must be negative)]. In the event of a positive pregnancy test result, the pregnancy must be reported to Emergent and the *National Smallpox Vaccine in Pregnancy Registry*. As a COVID-19 precautionary measure, women of childbearing potential will not be included in the study temporarily. Vaccination site inspection. If the visit cannot be performed in person, the study subject should take a photograph of the vaccination site or show it over live video call to the Investigator who will document the assessment. Photo or live video call will be deleted after assessment.
- Unanticipated problems.
- All adverse events including all cardiovascular adverse events (symptoms and signs).
- Diary card review and verification against AE collection above.
- Concomitant medications (see section [6.10](#)).
- Review vaccination site care instructions and provide vaccination site dressing kit (required only if the scab has not separated) (see section [6.2.3](#)).

6.8 Final Safety Assessment Day 90 (±3)

A final safety assessment will be conducted (a phone interview is acceptable if an in-person visit cannot be arranged) for the following:

- Identify if any exclusion criteria have arisen (i.e. skin conditions, living conditions/close contacts, pregnancy) (required only if the scab has not separated).
- Assessment of pericarditis/myocarditis symptoms (see section [6.9](#)).
- Unanticipated problems.

- All adverse events including all cardiovascular adverse events (symptoms and signs).

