- Thorough screening process to exclude subjects with higher risk of experiencing serious complications following vaccination e.g., excluding subjects with immunodeficiency, cardiovascular disease or heart condition, etc. (for a complete list see exclusion criteria section [4.2](#)).
- Vaccination of subjects who were previously vaccinated with a smallpox vaccine (Dryvax or ACAM2000) and who do not have any unresolved adverse events from previous smallpox vaccination.
- Exclusion of subjects who are pregnant or are planning to become pregnant and performing pregnancy tests at each study visit for women of childbearing potential.
- Safety evaluation at each study visit by assessments of pericarditis/myocarditis symptoms, adverse events and subject reminders for vaccination site care.
- An algorithm ([Appendix II](#)) for suspected pericarditis/myocarditis will be followed to ensure subject safety and follow-up. If a subject who needs to have an EKG performed at BPL is not able to complete an in-person study visit due to COVID-19 restrictions, he/she will be instructed to go to the nearest emergency room (ER). The subject will be required to bring back the medical records to the next protocol scheduled visit. If a subject is not able to obtain the records or attend

the visit in person then the copy of the medical records is to be requested from the ER and sent to the Principal Investigator.

- A final safety assessment at Day 90 post-vaccination. All related adverse events (AEs) (serious and non-serious) will be followed to resolution or stabilization as applicable (may extend beyond Day 90 post-vaccination).
- Safety of subjects will be monitored throughout their study participation utilizing a combination of centralized and onsite monitoring (risk-based monitoring approach). Sites will be monitored and data will be reviewed on a monthly basis according to a Medical Monitoring Plan. A Data and Safety Monitoring Board (DSMB) will be established to meet at pre-defined intervals and have ad hoc meetings (if necessary) to review study data and independently ensure the safety of subjects participating in this study according to the DSMB charter.

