4 SELECTION AND WITHDRAWAL OF SUBJECTS

4.1 Subject Inclusion Criteria

Subjects must meet the inclusion criteria to participate in the study.

- Signed written informed consent.
- Age 18 to 65
- Normal and healthy (immune competent) as determined by medical history, physical exam, vital signs and clinical laboratory tests during the screening period

- If the lab result for quantitative immunoglobulin A (IgA) is lower than 15% below normal range, the subject may not proceed further in the screening process.
- Subject must meet all required subject suitability criteria that pertain to normal source plasma donors as per 21 CFR 640.63.
- Negative human immunodeficiency virus (HIV) serology during screening period.
- Subject must have been previously immunized for smallpox, at ≥ 3 years prior to commencement of screening assessments, and vaccination history must be confirmed by oral or written history and the presence of a visible pathognomonic smallpox vaccination scar.
- Female subjects of childbearing potential must agree to use highly effective birth control methods. Acceptable methods of birth control include: IUD (inserted at least seven days prior to vaccination), hormonal implant (inserted at least 30 days prior to vaccination), oral contraceptive regimen (started at least 30 days prior to vaccination) and injectable hormone (injected at least 30 days prior to vaccination). The decision to allow use of hormonal contraceptives should be based on the potential for interactions with concomitant medications. Birth control method must be used throughout the study until scab separates. Females of non-childbearing potential are defined as being surgically sterile or meeting postmenopausal requirements and all women must be educated on risks of vaccine to an unborn child. Postmenopausal is defined as either >12 consecutive months with no menses without an alternative medical cause or $FSH \geq 40$ mIU/mL or if these criteria are not met and the woman is >50 years, she may participate if she agrees to undergo pregnancy testing requirements and agrees to use an effective birth control method such as barrier contraception for four weeks post-vaccination or until the scab separates, whichever is longer. Written confirmation is required for surgical sterility and birth control methods. As a COVID-19 precautionary measure, women of childbearing potential will not be included in the study temporarily.

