7.8.1 Anticipated Vaccine Reactogenicity and Adverse Events

The expected responses to re-vaccination with ACAM2000 are similar to the expected responses of primary vaccinia vaccination, except typically with less severity and shorter duration. In general, the shorter the interval between first-time vaccination and revaccination, the more likely it is that there will be no "take" or major reaction. Among those for whom 25 years or more has elapsed since last vaccination, essentially all should experience a "major reaction" indicative of a vaccination "take". Rarely, in some individuals, seemingly appropriate vaccination techniques may result in no reaction; these are considered as 'non-takes'.

The expected responses to vaccination "take" include:

- Reddening of the injection site within 30 minutes of administration.
- The development of a papule at the site of vaccination two to five days after percutaneous administration of vaccinia vaccine.
- The papule becomes vesicular, then pustular and reaches its maximum size in eight to ten days.
- The pustule dries and forms a scab, which separates within 14 to 21 days, leaving a scar.
- Local reactions at the inoculation site are expected, including redness, swelling, tenderness, pain and itchiness.
- Fever (approximately 15% of vaccinees are expected to develop a fever >100°F upon re-vaccination).

These reactions are typically mild ([Table 1](#)) and do not interfere with daily function. Any clinical observation that fit these criteria will not be characterized as adverse events.

Variations of expected reactions may occur in a small number of vaccinees including:

- Local satellite lesions (that are normal in appearance) and are within 2.5 cm (1 inch) of the vaccination site
- Lymphangitis
- Local edema
- Robust "take" (intense inflammation surrounding the papule)

None of these expected variations of normal reactions require any treatment other than symptomatic relief ([7](#)).

However, if an expected vaccine reaction is of greater intensity or duration (i.e., moderate or severe pain ([Table 1](#)), requires medication or interferes with daily life), these observations should be characterized as an adverse event.

Regardless of whether these observed vaccine site reactions are characterized as adverse events or not, the clinical observation should be noted in the donor record file.

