2. As described in Investigator's Brochure: In the ACAM2000 clinical studies 92% of previously vaccinated subjects, experienced one or more adverse event. Common events included injection site reactions (erythema, pruritus, pain and swelling) and constitutional symptoms (fatigue, malaise, feeling hot, rigors and exercise tolerance decreased). Across all ACAM2000 studies 3% of previously vaccinated subjects experienced at least one severe adverse event (defined as interfering with normal daily activities). In the event that 6% of vaccinated subjects report related expected AEs assessed as severe as per section 7.5 of the protocol an ad hoc DSMB meeting will occur.
3. If two pregnancies occur during the study.
 - ACAM2000 has not been studied in pregnant women. Live vaccinia virus vaccines can cause fetal vaccinia and/or fetal death.
 - Note: One pregnancy will result in a Cangene Corporation directed investigation, corrective actions and a Dear Investigator Letter to all study sites as noted in the VA-008 Medical Monitoring Plan.
4. If two secondary transmissions occur during the study.
 - ACAM2000 is a live vaccinia virus that can be transmitted to persons who have close contact with the vaccinee and the risks in contacts are the same as those stated for vaccinees.

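### After the Day 35 urine test, a woman whose scab is off and whose reactions have resolved is not systematically asked about pregnancy, so the count behind SAP 7 trigger 3 can be low

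*Protocol*

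**What the plan says.** **Testing.** The Schedule of Events has a serum test at screening and urine tests at baseline, Days 7, 12, 21, 28 and 35, and at extended weekly visits for unresolved reactions. There is no test at Day 3 or Day 90. The last routine one, in Protocol 6.6, is the "Urine pregnancy test for female subjects of child bearing potential". Protocol 1.2 nevertheless lists among the safety measures "performing pregnancy tests at each study visit for women of childbearing potential".

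**Day 90.** Protocol 6.8 and the synopsis carry one item that mentions pregnancy: "Identify if any exclusion criteria have arisen (i.e. skin conditions, living conditions/close contacts, pregnancy) (required only if the scab has not separated". Two other items apply whatever the scab status: unanticipated problems, and "All adverse events including all cardiovascular adverse events (symptoms and signs". The Schedule of Events shows no pregnancy entry at Day 90. Subjects without a take have no Day 90 contact (Protocol 6.4).

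**Scab timing.** Protocol 7.8.1: "The pustule dries and forms a scab, which separates within 14 to 21 days, leaving a scar". Appendix I adds that the course may be shorter on revaccination, and every subject is a revaccinee.

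**Contraception.** For women of childbearing potential, Protocol 4.1 says: "Birth control method must be used throughout the study until scab separates". For women over 50 who meet neither menopause criterion it gives "barrier contraception for four weeks post-vaccination or until the scab separates, whichever is longer".

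**Use of the count.** SAP 6 finds pregnant subjects from the summary of test results. SAP 7 calls an ad hoc DSMB meeting "If two pregnancies occur during the study", and a single pregnancy starts a sponsor investigation and a letter to all sites.

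**The concern.** The scab condition makes sense for the parts of the Day 90 item about skin conditions and close contacts, because the transmission precautions also last until the scab falls off. Pregnancy sits in the same item and inherits the condition. By the protocol's own timing almost no scab remains at Day 90, so the pregnancy question applies to almost nobody.

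SAP 7 notes that live vaccinia vaccines can cause fetal vaccinia or fetal death. Its two pregnancy safeguards work only if pregnancies are found. Any gap in finding them biases the count in one direction, downwards. The pregnancies most likely to be missed are those conceived just before the last test, which is also when the scab-based contraception wording may have lapsed.

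**Working it through.** The plan states no figure to reproduce. The check is a reading of the passages followed by date arithmetic.

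**1. Who is asked or tested after Day 35?**

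| Group | Contact after Day 35 | Pregnancy asked or tested? |
|---|---|---|
| Take, scab off, reactions resolved | Day 90 call or visit | No test; pregnancy item not required |
| Take, in extended weekly visits | Weekly, then Day 90 | Urine test weekly, whatever the scab status (6.7) |
| Take, scab still on at Day 90 | Day 90 call or visit | Pregnancy item required |
| No take | None | No |

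**2. Days without a routine test or question (first row).** Inputs: Day 35 (±3) and Day 90 (±3).
- Nominal: 90 − 35 = 55 days; 55/90 = 61% of the 90 days.
- Shortest: Day 38 to Day 87, 87 − 38 = 49 days.
- Longest: Day 32 to Day 93, 93 − 32 = 61 days.

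**3. Conceptions too late for the Day 35 test.** The documents give no detection lag. I assume a urine test turns positive 10 to 14 days after conception.
- Latest conception detectable at Day 35: 35 − 14 = Day 21 to 35 − 10 = Day 25.
- With the visit window: 32 − 14 = Day 18 to 38 − 10 = Day 28.
- Days before Day 35 that the test cannot cover: 10 to 14 of 35, or 29% to 40%.

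**4. Both readings of the study period in trigger 3.** Neither document defines it.
- *Ends at Day 35.* The visit is titled End of Study, and Protocol 9.2 treats donors past Day 35 with resolved events as having completed the trial. Step 3 still leaves conceptions from about Day 21 to 25 onward possibly negative at the last test.
- *Runs to Day 90.* SAP 1 adds a final safety assessment on Day 90, and Protocol 1.2 lists it as a safety measure. Steps 2 and 3 both apply: 90 − 25 = 65 to 90 − 21 = 69 days.

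**5. Would the open adverse event question catch a pregnancy?** Not dependably. Protocol 7.1 defines an adverse event as an untoward occurrence. The special-interest list in 7.4 has fetal vaccinia but not pregnancy. The visit sections start the report to the sponsor and the registry from a positive test. SAP 6 also works from tests, so a pregnancy mentioned at Day 90 has no stated route into the summary or the trigger.

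**6. What a Day 90 question would add.** Conceptions between about Day 21 and Day 35 lie 55 to 69 days before Day 90, well beyond the assumed lag. Under the same lag, conceptions from about Day 76 (90 − 14) to Day 80 (90 − 10) could still be unknown, so the gap narrows but does not close.

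**The case against.** - **The scab condition looks deliberate.** It recurs in the synopsis and in 6.7 and 6.8, and the note appended to the SAP describes the safety focus as running through scab separation. This stands as an explanation of the item as a whole. It does not explain why pregnancy, which feeds a DSMB trigger, should depend on it.
- **If the study ends at Day 35, schedule and trigger agree.** A reader might infer a plain conflict between SAP 7 and the test schedule. The documents do not support that, because the period is undefined and one reading aligns the two. Even on that reading, conceptions in the last 10 to 14 days before the test can be missed.
- **Later pregnancies are not wholly invisible.** A reader might infer that pregnancies after Day 35 go unascertained. That is too strong: women in extended visits are still tested, and Day 90 collects all adverse events and unanticipated problems. Systematic ascertainment is what is missing.
- **The contraception rule may not stop early.** A reader might infer that it ends at scab separation. The sentence names both the study and the scab as end points, so it is ambiguous rather than a clear cut-off.
- **Reach is limited.** Women of childbearing potential are temporarily not enrolled. This stands, and it limits the present effect.
- **The mismatch in 1.2 is editorial.** Largely so: Day 3 follows a negative baseline test. It still describes a safeguard the schedule does not deliver.

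**Conclusion.** The point holds in this form: for a woman whose scab is off and whose reactions have resolved, pregnancy is not systematically ascertained after Day 35 (±3). The uncovered stretch is 55 days (49 to 61). Under an assumed lag of 10 to 14 days, conceptions from about Day 21 to 25 can also escape the Day 35 test. The count used in SAP 7 can therefore be low on either reading of the study period.

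The size should not be overread. A reader might take 55 of 90 days as 61% of pregnancies missed. The documents give no pregnancy rate and no number of women at risk, so calendar days cannot be turned into missed cases. The lag is an outside assumption, shown as a range.

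The practical effect falls on reopening of enrollment, on any women of childbearing potential still in follow-up, and on women over 50 who meet neither menopause criterion. Protocol 4.1 places the last group within its postmenopausal definition while still requiring pregnancy tests, so the pause may not reach them. An amendment cannot recover women already past Day 90. The case for acting is that the remedy costs almost nothing.

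**What to change.** 1. **Protocol 6.8, synopsis and Schedule of Events.** Take pregnancy out of the scab-conditional item at Day 90. Ask pregnancy status and, if pregnant, estimated conception date of every woman subject to pregnancy testing, whatever the scab status.
2. **SAP 6 and SAP 7.** Count reported pregnancies as well as positive tests in the pregnancy summary and in trigger 3, and define the period over which pregnancies count.
3. **Protocol 1.2.** Correct the statement on testing at each visit so that it matches the schedule.
4. **Reconcile, for the sponsor to decide.** First, the contraception end date across 4.1, the synopsis and its footnotes a and b, and Schedule footnote g, including for women who never form a scab. Second, the Day 35 visit for subjects without a take: the synopsis allows a video or telephone contact while requiring a urine test, whereas 6.4 and Schedule footnote h require attendance in person. No duration or clinical rule is proposed here.

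**Cost.** One question at a contact that already takes place, with its data field, and wording in a protocol and SAP amendment; no extra test. Conceptions shortly before Day 90 would still be missed. Women without a take would still have no contact after Day 35. A further call to them is a trade-off, since the plan waives their Day 90 assessment, and it is not part of this recommendation.

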6.9 Additional Assessments for Subjects with Symptoms of Pericarditis and/or Myocarditis

In the event that a subject presents at any assessment with symptoms or findings suggestive of pericarditis and/or myocarditis (e.g., chest pain, heart palpitations, irregular heartbeat, excessive fatigue, peripheral edema, shortness of breath, unexplained syncope, dry cough) the investigator will conduct additional assessments (e.g., physical exam including pericardial rub, assess for diminished heart sounds, pleural effusion, and peripheral edema) as required to confirm or rule out a clinical diagnosis of pericarditis/myocarditis. If unable to perform additional assessments in person, subject will be referred to the ER for further evaluation.

If isolated symptom(s) is/are mild and not likely to be pericarditis and/or myocarditis the site will follow up with the subject after 24 to 48 hours to assess if the symptom(s) persists. If resolved, the subject may continue in the study according to the scheduled visits. Subjects should be instructed to report reoccurrence, worsening of, or presentation of additional symptoms immediately to the site physician.

If the subject symptom(s) is/are indicative of pericarditis and/or myocarditis at any visit or if after 24 to 48 hours the reassessment suggests the symptom(s) is/are persisting and/or worsening, the site will perform an EKG. The EKG will be interpreted by an off-site board certified cardiologist provided by the EKG supplier. If a subject is not able to make the in-person visits due to COVID-19 related travel restrictions, then the subject exhibiting potential symptoms of pericarditis/myocarditis needing an EKG will be referred to ER.

If following off-site cardiologist EKG review the subject is not likely to have pericarditis and/or myocarditis, the site will follow-up with the subject after 24 to 48 hours to assess if the symptom(s) persists. If resolved, the subject may continue in the study according to the scheduled visits. If after off-site cardiologist EKG review pericarditis and/or myocarditis is likely, the subject should immediately be referred to a local board-certified cardiologist for further assessment and follow-up where national criteria for evaluation and treatment based upon local standards of care will be applied.

If at any visit the subject symptom(s) is/are severe and indicative of pericarditis and/or myocarditis, the subject should immediately be referred to a local board certified cardiologist for further assessment and follow-up where national criteria for evaluation and treatment based upon local standards of care will be applied i.e., site EKG and off-site cardiologist review should not occur. For these expedited cases, EKG(s) should be interpreted by a local board-certified cardiologist who is aware of the patient's history and physical exam results.

The subject will be followed as described above for unresolved related adverse events. Subject should be made aware that any symptoms of pericarditis and/or myocarditis should be reported to the site physician immediately.

Refer to the algorithm provided in [Appendix II](#) for the required action steps if pericarditis and/or myocarditis are suspected.

